9.3 Treatment Conditions

9.3.1 HIV Usual Care (Both Arms)

All participants receive comprehensive HIV primary care, case management, addiction counseling, and social support services from HIV clinics as they would regardless of study participation. As part of protocol training, HIV clinic providers will be encouraged to offer ART within 4 weeks of randomization for participants not already prescribed ART. Current guidelines recommend offering ART to all HIV-infected participants, regardless of CD4 count (Thompson, Aberg et al. 2012). The schedule of medical care provided will be as deemed appropriate by the treating provider. HIV-infected participants are typically seen at least twice within the first month of initiating ART, and at least every 3 months thereafter for monitoring. Medical visits will not be considered study visits, though they may coincide with study visits. HIV clinic treatment will also include usual addiction counseling services, which are offered as a part of usual care in most large U.S. HIV clinics. As part of protocol training, HIV clinic providers will be asked to refer study participants to existing addiction counseling services in their clinic, as they would do regardless of study participation. Throughout the course of the trial, HIV clinics will be monitored for any potential changes that might occur in standard practice around medical management of HIV infection or addiction treatment services. HIV clinic medical and counseling visits will be tracked through medical record abstraction throughout study participation (See Section 10 Assessments).

9.3.2 Medical Management (When applicable)

Study clinicians will be trained in medical management (MM). MM is a brief counseling intervention delivered by non-addiction medical providers to improve response to medication-assisted addiction treatments delivered in medical settings (Pettinati and National Institute on Alcohol Abuse and Alcoholism (U.S.) 2004). It has augmented care for medication-assisted treatment of alcohol dependence with acamprosate and oral naltrexone in the COMBINE study (Anton, O'Malley et al. 2006), integration of XR-NTX treatment of alcohol dependence in primary care settings (Lee, Grossman et al. 2010), and integration of BUP/NX for treatment of opioid dependence in primary care (Fiellin, Pantalon et al. 2006). Since MM is meant to facilitate medication-assisted addiction treatment, it will be performed only for participants offered medication-assisted treatment in the HIV clinic (e.g. participants with opioid use disorders randomized to XR-NTX and TAU participants receiving clinic-based

buprenorphine/naloxone or methadone for opioid use disorder and those prescribed disulfiram, accamprosate, etc. for alcohol use disorder). TAU participants referred for off-site methadone maintenance or buprenorphine/naloxone will not receive MM since medical oversight is the responsibility of the treating provider. TAU participants who receive non-medication-assisted treatments such as 12- step groups or psychosocial counseling will not receive MM. During brief MM sessions, study clinicians will review recent drug and alcohol use, recommend abstinence, review medication side effects, and encourage adherence to medication-assisted treatment and participation in clinic and/or community support groups.

9.3.3 Clinic-based Extended-Release Naltrexone (XR-NTX)

9.3.3.1 XR-NTX Detoxification and Induction (0 - 4 weeks duration)

Following randomization, participants assigned to office-based XR-NTX will undergo detoxification and naltrexone induction in accordance with published guidelines (Asplund, Aaronson et al. 2004; Mayo-Smith, Beecher et al. 2004; Center for Substance Abuse Treatment 2006; Sigmon, Bisaga et al. 2012). Participating HIV providers will be trained to assess potential participants for the anticipated severity of opioid and alcohol withdrawal symptoms and manage outpatient detoxification procedures for participants with mild to moderate anticipated opioid or alcohol withdrawal severity. Participants with anticipated severe withdrawal symptoms (e.g., > 6 bags per day of heroin; >100 mg/day morphine equivalents prescription opioid use) will be referred to local detox facilities for medication-assisted inpatient detoxification that may involve opioid medications. Participants with anticipated severe alcohol withdrawal (increased risk of delirium tremens, seizures) should be admitted for inpatient detoxification. Guidelines for detoxification and induction onto XR-NTX are provided in study SOPs.

Prior to the naloxone challenge, participants randomized to XR-NTX must complete/have completed opioid detoxification, be at least 24 hours removed from the last dose of opioid agonist (heroin, prescription opioids, methadone or buprenorphine) and have a UDS negative for the extended opioid spectrum. If initial UDS is positive, UDS is repeated daily until negative. Only then will the naloxone/ challenge take place.

9.3.3.2 Naloxone Challenge

The naloxone challenge is performed to confirm the absence of opioids. Only those with recent opioid use are required to complete a naloxone challenge. The naloxone challenge consists of the delivery of 0.8 mg naloxone IV, with an observation period of 10-20 minutes. Heart rate and blood pressure measurements are completed prior to injection and 10-20 minutes post-injection, along with clinical assessment of opioid withdrawal symptoms. Significant changes in vital signs (blood pressure and heart rate) or signs of opioid withdrawal should be taken as a positive result of the challenge. If the challenge is positive, the participant should be encouraged to remain opioid abstinent and repeat the UDS and the naloxone challenge over the next several days. Participants may be re-challenged in this manner for up to one week. If participants do not have adequate peripheral venous access for IV naloxone administration, SC, intranasal, or IM administration is acceptable with the caveat that a 30-40 minute observation period be used, to account for longer absorption times. If no reaction to a naloxone challenge, the study clinician may proceed to XR- NTX injection.

9.3.3.3 Active Treatment with XR-NTX (Treatment Week 0 through Week 16)

Following a negative naloxone challenge, XR-NTX monthly injections will begin. XR-NTX (4cc, ~380mg of naltrexone base) will be administered approximately every four weeks (weeks 0, 4, 8, 12) for a maximum of 4 doses in the form of Vivitrol®, which will be obtained by NIDA or the NIDA contractor for distribution to the sites. XR-NTX will be administered by intramuscular injection to the buttocks (alternating sides monthly) according to the injection preparation and administration procedures specified in the Vivitrol® product package insert. These procedures are designed to minimize the risk of injection site reactions.

9.3.3.4 *Handling of Missed XR-NTX Doses, Lapses, and Relapses*

Use of illicit opioids presents different concerns in the management of participants receiving XR-NTX maintenance, compared to those receiving agonist therapy. A participant receiving XR-NTX may miss a scheduled injection, and resume opioid use. However, because of the long duration of action of XR-NTX (full blockade out to 5 weeks after the last injection (Comer, Collins et al. 2002)) a grace period of at least 7 days can be expected during which repeat XR-NTX injection can be rescheduled without risk of relapse. If the participant misses a scheduled injection and uses opioids during at least two of the seven days following the date of the scheduled injection, relapse will be suspected and the provider will perform a repeat naloxone challenge as described above. If the challenge is negative, XR-NTX administration will be resumed. If positive, then XR-NTX administration would risk precipitating withdrawal. However, because naltrexone blood levels remain and there is partial blockade beyond week 5, vulnerability to relapse may be more gradual, and the possibility of mild or equivocal reactions to naloxone challenge more common. In this instance, a second challenge within 72 hours will be attempted, and if tolerated, the next injection can be given. Missing a scheduled XR-NTX injection is the most important threat to the success of naltrexone maintenance. In the event of missing a scheduled injection, clinic study staff will contact the participant for follow up. The goal of these contacts is to re-establish commitment to the XR-NTX treatment and schedule a next injection as soon as possible. Participants who miss a scheduled XR-NTX dose but remain abstinent (i.e., return to clinic reporting no opioid use, urine negative for all opioids, and passing naloxone challenge), may be restarted on XR-NTX up to 3 weeks after the scheduled dose.

9.3.3.5 *Dispensing of XR-NTX*

Study medication (XR-NTX) will be provided by the study at no cost to the participant. XR-NTX will be administered in clinic at induction (week 0) and at treatment weeks 4, 8, and 12.

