4.1.1 Figure: Conceptual Model

4.2 Naltrexone (NTX) and Extended-Release Naltrexone (XR-NTX)

NTX is a potent opioid antagonist with high affinity for the mu-opioid receptor. In the U.S. it is approved for use in treating opioid dependence and alcohol dependence. It is highly efficacious in preventing relapse to opioid dependence provided that it is taken as prescribed, but adherence with oral naltrexone is problematic and leads to extremely high dropout rates, with the occasional exception of treatment in criminal justice and other settings where relapse may be linked to severe adverse consequences (Volpicelli, Rhines et al. 1997; O'Brien 2001; Rothenberg, Sullivan et al. 2002). This has led to intensive efforts - including NIDA- and NIAAA- funded grants to small businesses - to develop long-acting naltrexone preparations that can be administered as an injection or placed as an implant once per month or less frequently (NIDA 1976; Lobmaier, Kornor et al. 2008).

XR-NTX (Vivitrol[®], NTX-containing polylactide-co-glycolide [PLG] biodegradable sterile microspheres suspended in a diluent) is delivered by monthly injection into the muscles of the upper outer quadrant of the buttock. Each vial of microspheres contains 380 mg NTX which are suspended by adding a diluent that comes with the product and shaking for about a minute prior to injection of the full (less dead-space) content of the vial. Plasma concentrations of NTX and 6-beta naltrexol (its main active metabolite) after a single XR-NTX injection are detectable for at least 30 days. Consistent with this, in human laboratory studies with Vivitrol[®] and Depotrex[®], essentially complete blockade of opioid agonist effects is seen for 30 days (Comer, Collins et al. 2002; Bigelow, Preston et al. 2006). To maintain blockade beyond 30 days, XR-NTX must be re-administered. Long-term use of NTX and XR-NTX is not associated with tolerance, dependence, addiction or withdrawal on discontinuation. NTX and XR-NTX will, however, precipitate withdrawal in individuals physiologically dependent on opioids and decrease opioid tolerance.

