10.1 List of all CRF's and Table of Assessments

Assessment/Activity	Associated CRF	Pre-Screening	Screening	Baseline	Randomization	Week 0 (induction)	Week 1	Week 4	Week 8	Week 12	Week 16	End of Treatment (≠Week 16)	As Needed Only
Inclusion/Exclusion checklist	ENR-B				X								
Informed Consent/HIPAA	ENR-A		X										
Inventory Form	INV												X
Locator Form			X	X	X	X	X	X	X	X	X	X	
Master Enrollment Log			X	X									
Medical Release			X										X
Missed Visit Form	MFV												X
Pre-Screening Interview	PSI	X											
Progress Note Checklist			X	X	X	X	X	X	X	X	X	X	
Protocol Deviation	PDV												X
Screening Log		X											
Study Termination	STT										X	X	
Visit Compensation Log			X	X	X	X	X	X	X	X	X	X	
General Measures													
Demographics	DEM		X										
Quality of Life, from PhenX	QLP			X							X	X	
Tobacco Use History, from PhenX	TUH			X							X	X	
Safety & Medical Measures													
Adverse Events	AD1-3												X
ARV Medication Log	ARV			X							X	X	
CBC	LAB		X										
CD4 Count	LAB				X			X		X	X	X	
Confirmed Pregnancy and Outcome	PRG,PO1- 4												X
Detoxification	DTX					X							

Assessment/Activity	Associated CRF	Pre-Screening	Screening	Baseline	Randomization	Week 0 (induction)	Week 1	Week 4	Week 8	Week 12	Week 16	End of Treatment (≠Week 16)	As Needed Only
ECG Results	ECG		X										
Ethyl Glucuronide	UDS		X				X	X	X	X	X	X	
Fatal Overdose	FOD										X	X	
Vital Signs (blood pressure, pulse, temperature, height, and weight)	VIS		X								X	X	
Hepatitis B surface antigen (HBs AG)	LAB				X								
Hepatitis C virus antibody (HCV ab)	LAB				X								
Hepatitis C pcr confirmation, when HCV ab +	LAB												X
HIV-1 RNA PCR	LAB				X			X	X	X	X	X	
Injection Site Abnormality	INA												X
Injection Site Examination	INX						X	X	X	X	X	X	
LFT (AST, ALT) and INR	LAB		X				X	X	X	X	X	X	
Medical and Psychiatric History	MHX		X										
Medication Adherence	MAD			X				X	X	X	X	X	
Pain Assessment	PEG			X				X	X	X	X	X	
Naloxone Challenge	NXC					X*							
Non-Fatal Overdose	NFO			X							X	X	
PBMC	LAB				X			X					
Physical Examination	PEX		X										
Pregnancy and Birth Control Assessment	PBC		X			X	X	X	X	X	X	X	
UDS	UDS		X			X	X	X	X	X	X	X	
XR-NTX administration log	INJ					X		X	X	X			
XR-NTX Injection						X		X	X	X			
Drug Use, HIV & Psychological Measures													
ASI Lite Drug/Alcohol Use	ASD			X							X	X	
Concise Health Risk Tracking	CHRT			X		X	X	X	X	X	X	X	

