23.1.5.5 Study Specific Risks

XR-NTX blocks the effects of exogenous opioids after administration. After treatment, participants are likely to have reduced tolerance to opioids. Following Vivitrol® treatment, opioid use at the end of a dosing interval or after missing a dose could result in potentially life- threatening opioid intoxication (involving respiratory compromise or arrest, circulatory collapse, etc.) Attempting to overcome the blockade effects of Vivitrol® by administering large amounts of exogenous opioids is associated with potential risk of overdose. Participants in this study will receive an information card that will notify clinicians that they are receiving XR-NTX as part of a research study.

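### Section 9.3.3.4's seven-day grace period rests on five weeks of blockade where section 4.2 gives about 30 days, and the missed-dose naloxone challenge rules are inconsistent and incomplete

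*Protocol*

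**What the plan says.** **Schedule.** Section 9.3.3.3 says XR-NTX "will be administered approximately every four weeks (weeks 0, 4, 8, 12) for a maximum of 4 doses".

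**Missed doses.** Section 9.3.3.4 states that full blockade lasts to five weeks from the last injection, citing a 2002 depot naltrexone study, and concludes that "a grace period of at least 7 days can be expected during which repeat XR-NTX injection can be rescheduled without risk of relapse". If a participant misses the injection and "uses opioids during at least two of the seven days following the date of the scheduled injection, relapse will be suspected", the provider repeats the naloxone challenge. The section goes on to say that blockade is only partial past week 5, and it ranks a missed injection as the main threat to naltrexone maintenance. Participants who stayed abstinent "may be restarted on XR-NTX up to 3 weeks after the scheduled dose". Abstinent there means no reported opioid use, an opioid-negative urine and a passed challenge.

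**Blockade duration elsewhere.** Section 4.2 cites the same 2002 study and one other for near-complete blockade lasting 30 days, and adds: "To maintain blockade beyond 30 days, XR-NTX must be re-administered". Later in that section the blockade is again put at roughly 30 days.

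**General challenge rule.** Section 9.3.3.2 limits the required challenge to people whose opioid use is recent. It does not define recent.

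**Risk statement.** Section 23.1.5.5 warns that "opioid use at the end of a dosing interval or after missing a dose could result in potentially" life-threatening intoxication.

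**Schedule of assessments.** Table 10.1 marks "Naloxone Challenge" at Week 0 only, with no mark in its as-needed column.

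**The concern.** Section 9.3.3.4 is the text that sites follow when an injection is missed. Missed doses bear on two hazards that the protocol names: precipitated withdrawal on re-injection (sections 4.2 and 9.3.3.4) and overdose once blockade fades (section 23.1.5.5). The section reassures staff about a week, most of which another section places outside the blockade. It then gives challenge rules that neither cover every returning participant nor agree with the general rule two sections earlier.

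This matters first for participant safety and for consistent conduct at the two sites. It also touches outcomes. Precipitated withdrawal is a secondary safety outcome, and the share of the four expected doses received is the definition of XR-NTX retention, a primary outcome. If the two sites read the missed-dose text differently, they may differ in whom they challenge, whom they re-inject and when.

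**Working it through.** **Inputs**
- Dosing interval: 4 weeks = 28 days (section 9.3.3.3).
- Full blockade, missed-dose section: 5 weeks = 35 days (section 9.3.3.4).
- Blockade, background section: 30 days (section 4.2).
- Stated grace period: at least 7 days (section 9.3.3.4).

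**Formula.** Grace period = duration of blockade − dosing interval.

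**Step 1: reproduce the stated figure.** 35 − 28 = 7 days. This matches section 9.3.3.4 exactly, so the grace period depends on the five-week figure.

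**Step 2: use the protocol's other figure.** 30 − 28 = 2 days. Of the seven days after the scheduled date (days 29 to 35), days 29 and 30 are within the blockade and days 31 to 35 are not: 7 − 2 = 5 days uncovered. Section 4.2 does say that plasma levels stay detectable for at least 30 days, but that describes detectability and does not establish full blockade to day 35.

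**Step 3: read section 9.3.3.4 against itself.** The days said to carry no relapse risk are the same days on which two days of use lead the provider to suspect relapse. Both statements cannot hold as worded.

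**Step 4: list the challenge rules by opioid use after the missed date**
- No use: section 9.3.3.4 requires a passed challenge; section 9.3.3.2 requires none.
- Use on 1 of the 7 days: section 9.3.3.4 states no rule; under section 9.3.3.2 it depends on what counts as recent.
- Use on 2 to 7 of the 7 days: section 9.3.3.4 requires a repeat challenge.
- Use only after the seventh day: section 9.3.3.4 states no rule; under section 9.3.3.2 it again depends on what counts as recent.

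The trigger therefore counts only days 29 to 35, which section 9.3.3.4 treats as fully blocked. It does not count the later period, which the same section calls partly blocked. Participants enrolled for alcohol use disorder alone, who are eligible under section 7.1, fall in the no-use row if they take no opioids, so the two sections conflict for them as well.

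**The case against.** Several arguments for the protocol have force.

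- **Silence is not exemption.** A reader might infer that someone who used opioids on one day, or only after day 35, needs no challenge. The text does not say so. Section 9.3.3.2 can be read to require one, and section 9.3.3.4 refers back to the challenge procedure already described. This stands: the fault is an unstated rule and an undefined term. It does not remove the conflict, because the same general rule would release the abstinent participants whom section 9.3.3.4 makes pass a challenge. One can answer that a specific rule overrides a general one, but the protocol does not say that it does.
- **The three-week restart is conditional.** The latest restart is day 28 + 21 = 49, which is 14 days past the five-week figure and 19 past the 30-day figure. A reader might take this as the size of an unprotected window. It is not, because the permission covers only participants with no reported use, a negative urine and a passed challenge.
- **Relapse is not overdose.** Section 23.1.5.5 concerns intoxication when tolerance is reduced, and section 9.3.3.4 concerns relapse. Both could stand, so this tension is indirect. The direct conflicts are with section 4.2 and within section 9.3.3.4.
- **Timing of later doses.** Section 9.3.3.5 says "XR-NTX will be administered in clinic at induction (week 0) and at treatment weeks 4, 8, and 12", from which a reader might infer that a dose three weeks late must be followed by another after seven days, or that a delayed fourth dose would act beyond all safety follow-up. No passage directs the former, and section 9.3.3.3 makes the interval approximate. On the latter, section 22.4 continues adverse-event follow-up for 30 days after the last study visit. Neither inference is part of this point.
- **The synopsis's 28 days.** This describes how long a monthly injection lasts and is not a rival blockade figure.
- **Table 10.1.** The missing as-needed mark is clerical, since the text itself orders repeat challenges.

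**Conclusion.** The concern holds as an internal inconsistency in safety-relevant text. The protocol gives two durations of blockade that share a cited study, and its grace period is 7 days on one and 2 days on the other, a difference of 5 days in 7. The no-relapse-risk wording also contradicts the relapse trigger in the same section and sits uneasily with section 23.1.5.5. The challenge wording in sections 9.3.3.2 and 9.3.3.4 conflicts for abstinent returners and is unstated in 9.3.3.4 for two groups: use on one day, and use only after the seventh day.

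The verdict rests on the protocol's wording and a 28-day interval. The cited studies were not consulted, and no view is taken on which duration or challenge rule is right. It does not show that any participant would be re-injected without a challenge.

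The number affected cannot be computed, because the protocol gives no rate of missed doses. With at most 50 participants randomized 1:1, about 25 would be assigned to XR-NTX. No sample size, power or error rate is affected, and the effect on the retention and withdrawal outcomes is not quantified.

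**What to change.** Reconcile sections 4.2, 9.3.3.2, 9.3.3.4 and 23.1.5.5 so that:

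1. the protocol states one duration of blockade;
2. the grace-period statement, including its claim about relapse risk, agrees with that duration, with the relapse trigger in the same section and with the risk warning;
3. sections 9.3.3.2 and 9.3.3.4 together say which challenge rule applies to every participant who returns after a missed dose, and recent opioid use is defined if the term is kept;
4. Table 10.1 matches the result.

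Which duration and which clinical rules to adopt is for the sponsor's medical team to decide. The cost is small: revised protocol and SOP wording, a table correction and retraining at two sites.

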9.3.4 Treatment as Usual (TAU)

Participants assigned to the TAU group will receive the standard treatment for alcohol and opioid use disorders provided at each HIV clinic. The standard of care in U.S. and Canadian HIV clinics is currently to link with opioid agonist treatment services. Opioid substitution therapy is recommended for HIV-infected participants with opioid dependence (Thompson, Aberg et al. 2012; Thompson, Mugavero et al. 2012), and many HIV practices are being encouraged to adopt clinic-based BUP/NX (HIV/AIDS Bureau Special Projects of National Significance Program 2012). The standard of care for treatment of alcohol use disorders in HIV clinics is referral to detoxification, if needed, as well as outpatient or inpatient rehabilitation programs and 12-step groups, and/or on-site substance abuse counseling services. Medication-assisted treatment of alcohol use disorders with naltrexone, disulfiram, or acamprosate is rare in HIV clinics.

Many HIV clinics receive funding from the Ryan White Care Act for case management and addiction/mental health counseling services to facilitate engagement of HIV-infected patients with substance use disorders in treatment. In a 6-month randomized trial of methadone maintenance referral strategies, passive referral of heroin users resulted in 8% methadone maintenance enrollment at 6 months vs. 29% enrollment among those randomized to case-management assisted referrals ($p = .006$) (Coviello, Zanis et al. 2006).

Methadone maintenance referrals in HIV clinics may more closely approximate case-managed referral enrollment due to the presence of Ryan White Care Act-funded case managers and counselors.

During the formal site selection process, a thorough assessment will be conducted of each site's standard practice for linkage to addiction treatment services. Throughout the course of the trial, HIV clinics will be monitored for any potential changes that might occur in standard practice around linking HIV-infected clinic patients to substance use treatment.

